1.9 Rationale for Correlative Research

1.91 Recent successes of anti-PD-1/PD-L1 checkpoint inhibitors (e.g., pembrolizumab, and nivolumab) have reinvigorated the field of cancer immunotherapy (Hamid O, et. al., 2013 and Rizvi NA, et. al., 2015)^{20, 21}. Response rates have ranged from 13% to 37% in patients with progressive cancers that have failed multiple lines of therapy. Post-trial analyses have attempted to define molecular markers that correlate with tumor regression. Response to nivolumab was associated most strongly with expression of PD-L1 by the tumor and did not significantly correlate with infiltrating lymphocytes. PD-1 was expressed by tumor-infiltrating lymphocytes in 7/10 of responders and 9/18 non-responders and did not significantly correlate with a clinical response (Taube JM et. al., 2014)²². In contrast, response to pembrolizumab was strongly associated with a high frequency of CD8⁺ or PD-1⁺ T cells, either at the invasive margin or infiltrating the tumor, and, to a lesser degree, expression of PD-L1 (Tumeh PC, et. al., 2014)²³. In the proposed correlative research studies, we will assess CD8⁺ and PD-1⁺ T cell frequency and expression of PD-L1 and PD-L2 by tumor and associated leukocytes in primary tumor samples and pre-treatment

biopsies by immunohistochemistry. We will also assess PD-1 expression and its functional consequences in peripheral blood leukocytes before and throughout treatment using flow cytometry.

- 1.92 Tregs have been shown to express both PD-1 and PD-L1, and blockade of PD-1/PD-L1 interactions is thought to inhibit the induction, maintenance, and function of Tregs (Duraismamy J, et. al., 2013)^{9, 11}. A number of studies have investigated the effects of multi-target tyrosine kinase inhibitors on the immune system. Inhibition of VEGF activity by anti-VEGFR-2 antibody treatment inhibits Treg proliferation (Terme M, et. al., 2013)¹⁴. Sorafenib, a multikinase inhibitor that targets VEGFR-2, has been shown to inhibit Treg suppression *in vitro* and reduce the number of peripheral Tregs in cancer patients (Busse A, et. al., 2011 and Cabrera R, et. al., 2013)^{15, 16}. Thus, both pembrolizumab and lenvatinib may inhibit the suppressive effects of tumor-associated Tregs. We plan to investigate whether the frequency of FoxP3⁺ Tregs in the primary tumor and pre-treatment biopsy, as determined by immunohistochemistry for FoxP3, correlates with response to treatment. We will also investigate the frequency and phenotype of Tregs in peripheral blood before and throughout treatment using flow cytometry.
- 1.93 Tumor associated macrophages (TAM) and immature dendritic cells (iDC) have been described in primary thyroid tumors. Increased frequencies of TAM were associated with lymph node metastasis in patients with DTC (Qing W, et. al., 2012)²⁴. TAM in DTC expressed CD163 and IL-10 and have been proposed to play a role in tumor progression (Qing W, et. al., 2012)²⁴. CD1a⁺ iDCs were also found at high frequencies in DTC samples (Batistatou A, et. al, 2002, Ugolini C, et. al. 2007, and Scarpino S, et. al., 2000)²⁵⁻²⁷. We identified PD-L1⁺ TAM in 12/15 pT4 DTC and PDTC samples. Pro-angiogenic VEGFA is well documented in its ability to inhibit DC maturation and support the generation of TAM and myeloid derived suppressor cells (MDSC) (Alfaro C, et. al., 2009, Almand B., et. al., 2000, Dikov MM, et. al., 2005, Gabrilovich D, et. al., 1998, Voron T, et. al., 2014)²⁸⁻³². This immunosuppressive cellular network likely supports induction and maintenance of Tregs within the tumor microenvironment through production of IL-10 and TGFβ (Coffelt SB, et. al., 2011, Ghiringhelli F, et. al., 2005, and Huang B, et. al., 2006)³³⁻³⁵. We plan to investigate the frequency and phenotype of TAM and MDSC in tumor and blood samples, respectively.
- 1.94 Approximately 25% of patients with DTC produce thyroid-specific antibodies, most commonly against Tg and TPO (Fiore E, et. al., 2009 and Pacini F, et. al., 1988)^{36, 37}. We predict that titers of these autoantibodies may be surrogate markers for the anti-tumor response with pembrolizumab and lenvatinib therapy.
- 1.95 Recent analyses of patients with melanoma that underwent treatment with anti-PD-1 (pembrolizumab, Merck) revealed a strong positive association between the number of mutations in the tumor and responsiveness to the checkpoint blockade therapy (Rizvi NA, et. al., 2015)³⁸. While thyroid cancer, in general, is thought to be a have a low mutation burden, little is known about mutation frequency and antigenicity in more aggressive and metastatic cases. Here, we propose to investigate whether high frequency of mutations or type of mutation is associated with response to combination therapy.

- 1.96 It is likely that a subset of patients will not respond to treatment and will require alternative therapies. Numerous tumor-intrinsic and tumor-extrinsic factors will undoubtedly contribute to resistance (e.g., mutation load, MHCII expression, antigen presentation, immune suppressive factors). We plan to compare gene expression profiles by RNA-Seq from responders and non-responders using pre-treatment frozen and FFPE biopsy samples.

2.0 Goals

2.1 Primary

- 2.11 To investigate the clinical efficacy, as indicated by the rate of complete response (CR) per RECIST 1.1, of combination therapy with pembrolizumab and lenvatinib in lenvatinib-naïve patients with progressive radioiodine-refractory DTC (Cohort 1).
- 2.12 To determine the overall response rate (ORR) by the addition of pembrolizumab to patients with radioiodine-refractory DTC who have progressive disease on lenvatinib alone (Cohort 2).

2.2 Secondary

- 2.21 To determine the safety profile and toxicity of combination therapy with pembrolizumab and lenvatinib in patients with progressive DTC. (Cohort 1 and Cohort 2)
- 2.22 To determine progression-free survival (PFS) and overall survival (OS). (Cohort 1 and Cohort 2)

2.3 Correlative Research

- 2.31 To correlate tumor response (RECIST 1.1) with pretreatment frequency of CD8⁺ T cells in the primary and/or metastatic tumor. FFPE tumor samples will be evaluated for CD8⁺ T cells by immunohistochemistry. Staining intensity is scored on a 1⁺ to 3⁺ scale, and the percentage of positive cells per total lymphocytes is estimated (1 = <1%, 2 = 1-10%, 3 = 11-33%, 4 = 34-66%, 5 = 67-100%). Allred scores (intensity + percent positive) are generated for comparison between samples (Phillips T, et. al., 2007). Quantitation of the CD8⁺ cells will be performed using the Aperio Scanscope AT2 system (20X, 0.5 μm/pixel resolution). Our collaborating pathologist will designate both peritumoral and intratumoral areas for differential quantitation using the Aperio ImageScope application, and annotated regions will be analyzed for positive staining using an Aperio colormetric thresholding algorithm. To extrapolate the number of positive cells per mm², 15 random cells will be chosen to determine the average pixels per positive CD8 event. The average number of CD8 pixels will be divided by the total positive pixels to determine the number of positive CD8 cells in the annotated regions. The number of CD8 cells divided by the area will estimate the number of positive cells per mm². (Cohort 1 and 2)
- 2.32 To correlate tumor response (RECIST 1.1) with pretreatment PD-L1 and PD-L2 levels in the primary and/or metastatic tumor. Tumors will be evaluated for PD-L1 (by QualTek Clinical Laboratories) and anti-PD-L2 (Biogen M1H18) by immunohistochemistry, as described above. (Cohort 1 and 2)
- 2.33 To correlate tumor response (RECIST 1.1) with pretreatment frequency of lymphocytes expressing CD3, CD4, PD-1, FoxP3, or CD20, and of CD163⁺

macrophages. Cells types will be detected in pretreatment FFPE tumor tissue by immunohistochemistry. (Cohort 1 and 2)

- 2.34 To correlate tumor response (RECIST 1.1) with the phenotype and frequency of key leukocyte subsets (i.e., PD-1+ T cells, Tregs, myeloid subsets) in the peripheral blood before, at 6 and 18 weeks on therapy, and at 54 weeks (study completion), PD, or study withdrawal. Peripheral blood mononuclear cells and neutrophils will be isolated concomitantly by density gradient from peripheral blood, cryopreserved, and analyzed by 10-color flow cytometry. (Cohort 1)
- 2.35 To correlate tumor response (RECIST 1.1) with PD-1+ T cell functional capacity. Stimulated cytokine assays will be performed on lymphocyte populations isolated from peripheral blood, as described in 2.34. Briefly, cells will be stimulated with PMA/ionomycin or plate-bound anti-CD3 plus soluble anti-CD28 for 6 hours in the presence of brefeldin A and intracellular expression levels of IL-2, IFN γ , and TNF α will be determined by flow cytometry. Normal peripheral blood will be used as a control for optimal cytokine production. Patient T cell function will be compared before and after treatment. (Cohort 1)
- 2.36 To correlate tumor response (RECIST 1.1) with serum anti-thyroglobulin antibody levels assessed before, and at 18 weeks on therapy. (Cohort 1 and 2)
- 2.37 To correlate tumor response (RECIST 1.1) with tumor mutation status. Tumor mutation analysis will be performed by whole exome sequencing with DNA isolated from pre-treatment frozen biopsies and FFPE archival primary tumor for each patient where available, using patient-matched blood as a baseline control. (Cohort 1)
- 2.38 To broadly investigate mechanisms of response and resistance to combination therapy, gene expression profiles will be generated from frozen biopsies for analysis by RNA-Seq. Total RNA will be isolated with the RNeasy kit (Qiagen) and 500ng of RNA will be submitted mRNA-seq library construction (TruSeq Stranded mRNA Library Kit, Illumina). In parallel, FFPE primary tumor samples will be analyzed by RNA-Seq (Graw S, et. al., 2015)⁴⁰. (Cohort 1)

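### Section 2.31 reverses the division in the CD8+ image-analysis count, so the rule as written gives the reciprocal of the number of cells

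*Combined protocol and SAP*

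**What the plan says.** Section 2.31 describes two readouts of CD8+ T cells in FFPE tumour tissue. The first is an Allred score; these scores "are generated for comparison between samples". The second is an image-analysis count, "performed using the Aperio Scanscope AT2 system (20X, 0.5" µm per pixel), made separately in peritumoral and intratumoral regions marked by a pathologist.

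The count is built in three steps:

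- The aim is a density, introduced by the words "To extrapolate the number of positive cells per mm"². As the first step towards it, "15 random cells will be chosen to determine the average pixels per positive CD8 event".
- Within each marked region the count is then formed: "The average number of CD8 pixels will be divided by the total positive pixels to determine the number of positive CD8 cells".
- Last comes the density: "The number of CD8 cells divided by the area will estimate the number of positive cells", expressed per mm².

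No other section restates or corrects the second step. Section 17.31 refers back to section 2.3 for how submitted tissue is to be analysed, so section 2.31 is the protocol's operative description of the method.

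**The concern.** The second step divides a per-cell average by a total. That cannot give a number of cells; the total has to be divided by the per-cell average. The third step then carries the error into the density.

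If the sentence were followed literally, the count would fall as CD8+ staining rose, and samples would be ranked by count in exactly the reverse of the true order. Direction matters for this marker. Section 1.91 gives as background that "response to pembrolizumab was strongly associated with a high frequency of CD8"⁺ or PD-1⁺ T cells, and section 16.4 plans to relate CD8+ data to response, PFS and OS. An inverted marker could reverse the sign of an association.

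**Working it through.** The plan reports no numerical result for this step, so there is no figure to reproduce. The check uses units first and then an illustration.

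**Inputs**

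- a = average pixels per positive CD8 event, in pixels per cell (section 2.31, from 15 cells; no value given).
- T = total positive pixels in the annotated region, in pixels (section 2.31; no value given).
- Resolution = 0.5 µm per pixel (section 2.31).
- Positive fraction, pixels per event and region area: assumed below, because the documents give none.

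**Units**

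- As written: a/T = (pixels/cell)/pixels = 1/cells, which is 1/N.
- Intended: T/a = pixels/(pixels/cell) = cells, which is N.

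This holds for any positive a and T. Reading the average as plain pixels does not rescue the sentence, since pixels divided by pixels is a fraction and not a number of cells.

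**Illustration**

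Pixels per mm²: (1000/0.5)² = 4,000,000. In a 1 mm² region, 1% positive gives T = 40,000 and 2% positive gives T = 80,000. At 0.25 µm² per pixel, events of 100, 200 and 400 pixels cover 25, 50 and 100 µm².

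| Positive area | a (pixels per cell) | Correct count T/a | As written a/T |
|---|---|---|---|
| 1% | 100 | 400 | 0.0025 |
| 1% | 200 | 200 | 0.005 |
| 1% | 400 | 100 | 0.01 |
| 2% | 100 | 800 | 0.00125 |
| 2% | 200 | 400 | 0.0025 |
| 2% | 400 | 200 | 0.005 |

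The two columns multiply to 1 in every row. The written value is the reciprocal of the correct one, so it reverses the ranking of counts exactly. It is below 1 whenever T exceeds a.

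**Density**

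Let A be the area in mm² and D = N/A the correct density. The third step applied to 1/N gives 1/(N × A) = 1/(D × A²). The effect on the ranking of densities depends on the areas:

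- D = 100 with A = 1 gives 0.01, and D = 1,000 with A = 2 gives 1/(1,000 × 4) = 0.00025. The order is reversed.
- D = 100 with A = 10 gives 1/(100 × 100) = 0.0001, and D = 1,000 with A = 1 gives 0.001. The order is kept.

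With equal areas the density order is always reversed. With unequal areas it may or may not be, and the documents do not say how area varies.

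**The case against.** The best case on the other side is that this is a copy-editing slip and no result is wrong. The sentences on either side define pixels per event and cells per mm², and only T/a fits between them. A laboratory would almost certainly compute T/a, and a count of 0.005 cells would be caught at the first sample. The exact reversal applies to the count, which is an intermediate quantity, and not in general to the density, which is the stated output. The Allred score gives a second CD8+ measure, correctly defined, on the same tissue. Section 16.4 describes all the translational analyses as descriptive and hypothesis-generating. The illustration rests on assumed inputs, and the reciprocal relation is an identity that measures no effect on this trial.

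All of that stands as an argument about size, and it is why the point is rated minor. It does not make the sentence right. A complete, unambiguous calculation rule in the governing section cannot produce the quantity it names, and nothing elsewhere corrects it.

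**Conclusion.** The point holds: the count rule in section 2.31 is inverted as written and returns 1/N for N. The conclusion follows from the units alone and needs none of the assumed values, which serve only to show scale. The severity is minor. The error matters only if the sentence is applied literally, and then only for the image-analysis CD8+ readout (peritumoral and intratumoral) and the density derived from it. No claim is made that density rankings would be reversed in general.

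**What to change.** Swap the operands. Suggested wording: *For each annotated region, the number of CD8+ cells is estimated as the total positive pixels divided by the mean number of pixels per positive CD8 event.* The density sentence that follows needs no change.

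Section 2.32 says its markers are assessed "by immunohistochemistry, as described above", without saying whether the pixel-count method is included, and section 2.33 does not mention that method. If it is reused for other markers, the corrected formula should apply there too.

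The cost is one sentence. No new data are needed, and no endpoint, sample size or decision rule changes.

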3.0 Patient Eligibility

*No waivers of eligibility per ACCRU

3.1 Inclusion Criteria

- 3.11 Age \geq 18 years.
- 3.12 Locally recurrent and unresectable and/or distant metastatic differentiated thyroid cancer (DTC), histologically or cytologically confirmed. The diagnosis of DTC includes the following subtypes: Papillary thyroid cancer (PTC) (including but not limited to variants such as follicular variant, tall cell, columnar cell, Hürthle cell variant of papillary carcinoma, and poorly differentiated), Follicular thyroid cancer (FTC), including Insular variant, Hürthle cell carcinoma and poorly differentiated thyroid cancer.
- 3.13 Measurable disease meeting the following criteria (see Section 11.0):
 - 3.13a At least 1 lesion of \geq 1.0 cm in the longest diameter for a non-lymph node or \geq 1.5 cm in the short-axis diameter for a lymph node which is

serially measurable according to RECIST 1.1 using computerized tomography/magnetic resonance imaging (CT/MRI). If there is only one target lesion and it is a non-lymph node, it should have a longest diameter of ≥ 1.5 cm.

- 3.13b. Lesions that have had external beam radiotherapy (EBRT) or loco-regional therapies such as radiofrequency (RF) ablation must show evidence of progressive disease based on RECIST 1.1 to be deemed a target lesion.
- 3.14 For Cohort 1 Only: Evidence of disease progression ≤ 14 months prior to registration according to RECIST 1.1, as confirmed by the site study PI.
- 3.15 For Cohort 2 Only: Progressive disease (PD) on lenvatinib per RECIST 1.1 ≤ 60 days prior to registration, as confirmed by the site study PI. Patients need to have documented imaging and measurement of RECIST target lesions within 30 days of starting pembrolizumab.
- 3.16 Radioiodine (RAI)-resistant disease as defined by one or more of the following criteria:
- a. One or more measurable lesions that do not demonstrate RAI uptake
 - b. One or more measurable lesions progressive by RECIST 1.1 ≤ 14 months of prior RAI therapy.
 - c. One or more measurable lesions present after cumulative RAI dose of ≥ 600 mCi.
 - d. One or more measurable lesions that are FDG-avid (>5 SUV), if PET/CT scan performed. These lesions may also be RAI-avid.
- 3.17 ECOG Performance Status (PS) 0 or 1. (Form is available on the ACCRU web site)

- 3.18 The following laboratory values obtained ≤ 30 days prior to registration, unless otherwise specified:

System	Laboratory Value
Hematological	
Absolute neutrophil count (ANC)	$\geq 1,500$ /mcL
Platelets	$\geq 100,000$ / mcL
Hemoglobin	≥ 9 g/dL or ≥ 5.6 mmol/L without transfusion or erythropoietin dependency (≤ 7 days prior to registration)
Renal	
Serum creatinine OR Measured or calculated ^a creatinine clearance (GFR can also be used in place of creatinine or CrCl)	≤ 1.5 X upper limit of normal (ULN) OR ≥ 60 mL/min for subject with creatinine levels > 1.5 X institutional ULN
Hepatic	
Serum total bilirubin	≤ 1.5 X ULN OR Direct bilirubin \leq ULN for subjects with total bilirubin levels > 1.5 ULN
AST (SGOT) and ALT (SGPT)	≤ 2.5 X ULN OR ≤ 5 X ULN for subjects with liver metastases
Albumin	≥ 2.5 mg/dL
Coagulation	
International Normalized Ratio (INR) or Prothrombin Time (PT)	≤ 1.5 X ULN unless subject is receiving anticoagulant therapy as long as PT or PTT is within therapeutic range of intended use of anticoagulants
Activated Partial Thromboplastin Time (aPTT)	≤ 1.5 X ULN unless subject is receiving anticoagulant therapy as long as PT or PTT is within therapeutic range of intended use of anticoagulants
^a Creatinine clearance should be calculated per institutional standard.	

- 3.19a Adequately controlled blood pressure with or without antihypertensive medications defined as BP $< 150/90$ mmHg at screening.
- 3.19b Negative pregnancy test done ≤ 7 days prior to registration, for women of childbearing potential only.
- 3.19c Ability to complete Patient Medication and Blood Pressure diaries by themselves or with assistance.
- 3.19d Willing and able to provide informed written consent.

- 3.19e Willing to return to enrolling institution for follow-up (during the Active Monitoring Phase of the study).

*Note: During the **Active Monitoring** Phase of a study (i.e., active treatment and observation), participants must be willing to return to the consenting institution for follow-up.*

- 3.19f Willing to provide tissue and blood samples for correlative research purposes.(see Sections 6.12, 14.1 and 17.11).

3.2 Exclusion Criteria

- 3.21 **Cohort 1 only:** Prior treatment with previous VEGFR active multikinase inhibitor.
- 3.22 **Cohort 2 only:** Discontinued lenvatinib due to toxicity.
- 3.23 Pregnant or breastfeeding, or expecting to conceive or father children within the projected duration of the trial, starting with the pre-screening or screening visit through 120 days after the last dose of trial treatment.
- 3.24 Female subjects of childbearing potential: Unwilling or unable to use 2 methods of birth control or be surgically sterile, or abstain from heterosexual activity for the course of the study through 120 days after the last dose of study medication. NOTE: Subjects of childbearing potential are those who have not been surgically sterilized or have not been free from menses for > 1 year.
- 3.25 Male subjects: Unwilling or unable to use an adequate method of contraception starting with the first dose of study therapy through 120 days after the last dose of study therapy.
- 3.26 Co-morbid systemic illnesses or other severe concurrent disease which, in the judgment of the investigator, would make the patient inappropriate for entry into this study or interfere significantly with the proper assessment of safety and toxicity of the prescribed regimens.
- 3.27 Immunocompromised patients and patients known to be HIV positive (HIV 1/2 antibodies) and currently receiving antiretroviral therapy.
- 3.28 Currently participating and receiving study therapy (except lenvatinib for patients in Cohort 2) or has participated in a study of an investigational agent and received study therapy within 4 weeks prior to registration.
- 3.29a Diagnosis of immunodeficiency or is receiving systemic steroid therapy or any other form of immunosuppressive therapy ≤ 7 days prior to the first dose of trial treatment.
- 3.29b Known history of active TB (Bacillus Tuberculosis)
- 3.29c Hypersensitivity to pembrolizumab or any of its excipients.

- 3.29d Prior anti-cancer monoclonal antibody (mAb) ≤ 4 weeks prior to registration or who has not recovered (i.e., \leq Grade 1 or at baseline) from adverse events due to agents administered ≥ 4 weeks prior to registration.
- 3.29e Prior chemotherapy, targeted small molecule therapy, or radiation therapy within 2 weeks prior to study Day 1 (except lenvatinib for patients in Cohort 2) or who has not recovered (i.e., \leq Grade 1 or at baseline) from adverse events due to a previously administered agent.

NOTE:

- Subjects with \leq Grade 2 neuropathy are an exception to this criterion and may qualify for the study.
 - If subject received major surgery, they must have recovered adequately from the toxicity and/or complications from the intervention prior to registration, as deemed by treating investigator or site PI.
- 3.29f Known additional malignancy that is progressing or requires active treatment. Exceptions include basal cell carcinoma of the skin or squamous cell carcinoma of the skin that has undergone potentially curative therapy or in situ cervical cancer.
- 3.29g Known active central nervous system (CNS) metastases and/or carcinomatous meningitis. NOTE: Subjects with previously treated brain metastases may participate provided they are stable (without evidence of progression by imaging for at least four weeks prior to the first dose of trial treatment and any neurologic symptoms have returned to baseline), have no evidence of new or enlarging brain metastases, and are not using steroids for ≥ 7 days prior to trial treatment. This exception does not include carcinomatous meningitis which is excluded regardless of clinical stability.
- 3.29h Active autoimmune disease that has required systemic treatment in the past 2 years (i.e. with use of disease modifying agents, corticosteroids or immunosuppressive drugs). NOTE: Replacement therapy (eg., thyroxine, insulin, or physiologic corticosteroid replacement therapy for adrenal or pituitary insufficiency, etc.) is not considered a form of systemic treatment.
- 3.29i Known history of, or any evidence of active, non-infectious pneumonitis that required steroids.
- 3.29j Active infection requiring systemic therapy.
- 3.29k History or current evidence of any condition, therapy, or laboratory abnormality that might confound the results of the trial, interfere with the subject's participation for the full duration of the trial, or is not in the best interest of the subject to participate, in the opinion of the treating investigator.
- 3.29l Known psychiatric or substance abuse disorders that would interfere with cooperation with the requirements of the trial.
- 3.29m Received prior therapy with an anti-PD-1, anti-PD-L1, or anti-PD-L2 agent.

- 3.29n Known active Hepatitis B (e.g., HBsAg reactive) or Hepatitis C (e.g., HCV RNA [qualitative] is detected).
- 3.29o Received a live vaccine ≤ 30 days of planned start of study therapy. NOTE: Seasonal influenza vaccines for injection are generally inactivated flu vaccines and are allowed; however intranasal influenza vaccines (e.g., Flu-Mist®) are live attenuated vaccines, and are not allowed.
- 3.29p Proteinuria $>1+$ on dipstick urinalysis. Patients with $>1+$ proteinuria on dipstick urinalysis will undergo 24-hour urine collection for quantitative assessment. NOTE: Patients with > 1 g/24 hours will be ineligible.
- 3.29q Clinically significant gastrointestinal malabsorption syndrome.
- 3.29r New York Heart Association congestive heart failure of grade II or above, unstable angina, myocardial infarction within the past 6 months, or serious cardiac arrhythmia associated with significant cardiovascular impairment within the past 6 months. EF by MUGA or echo should not be less than the institutional lower limit of normal.
- 3.29s QTc prolongation > 480 msec, as calculated by either the Bazett or Fridericia formula, as per institutional standard.
- 3.29t Active hemoptysis (bright red blood > 1 teaspoon on more than one occasion) ≤ 3 weeks prior to registration.
- 3.29u **Cohort 2 only:** More than one prior treatment with VEGFR active multikinase inhibitor prior to original start of lenvatinib.

MUGA or Echocardiogram	X								X		
EKG	X				X				X		
Tumor measurement	X				X ⁵			X ⁵			X ⁵
Mandatory blood sample (Cohort 1; see Section 14.0)		X ^{R, 6}			X ^{R, 6}	X ^{R, 6}					X ^{R, 6}
Mandatory blood sample (Cohort 2)		X ¹²									
Mandatory serum sample (Cohorts 1 and 2; see Section 14.0)		X ^{R, 6}					X ^{R, 6}				
Mandatory archival surgical tissue sample (Cohorts 1 and 2; see Section 17.3)	X ^{R, 7}										
Optional tissue biopsy (Cohort 1; see Section 17.3)		X ^{R, 8}									
Patient Medication Diary			X ¹¹	X ¹¹	X ¹¹			X ¹¹	X ¹¹	X ¹¹	
Patient Blood Pressure Diary			X ¹¹	X ¹¹	X ¹¹			X ¹¹	X ¹¹	X ¹¹	

† Observation Phase: Part of the Active Monitoring Phase of a study. The time period following the active treatment phase when the participant continues to receive cycles of evaluation in compliance with the Test Schedule. Participants will be required to return to the consenting site for follow-up. Time frame is +/- two weeks.

* Cycles 23 – 35 apply only to those patients who extend treatment for up to an additional 12 months beyond the initial 54-week treatment period.

¹ Patients should be instructed to monitor BP at home three times/week at a minimum, and notify treating team if systolic BP \geq 160 mmHg and/or diastolic BP \geq 100 mmHg.

² PT/INR and PTT are only necessary at baseline, and as clinically indicated.

- ³ For women of childbearing potential only. Must be done ≤ 7 days prior to registration. This can be done by either blood or urine test, at the physician's discretion.
- ⁴ Check TSH and free T4 at baseline, then every other cycle starting with Cycle 3 then cycles 5 & 7 (day 1), then every 4th cycle starting with Cycles 11, 15 and 19 (day 1) for up to 54 weeks for all patients. For those patients who continue treatment beyond 54 weeks (up to an additional 12 months), continue checking TSH and free T4 on cycle 23, 27, 31 and 35. For those patients who do NOT have anti-thyroglobulin antibodies, check thyroglobulin at baseline, and then same time points as TSH and free T4.
- ⁵ Imaging is to be performed day 1 for Cycles 3, 5, and 7, then every 4th cycle for Cycles 11, 15, and 19, up to 54 weeks. Scans can be done sooner than 18 weeks if clinically indicated. (See Section 13 for further details.) For those patients who continue treatment beyond 54 weeks (up to an additional 12 months), imaging should be done on Cycle 23, 27, 31 and 35. CT or MRI scans of the neck, chest, abdomen and pelvis, as determined by the investigator to assess response per RECIST v1.1. Imaging with IV contrast is encouraged but will be done per investigator's discretion. If the abdomen-pelvic CT is negative at baseline, subsequent imaging of this site is required only if clinically indicated during the study period. NOTE: Use same imaging throughout the study as much as possible. PET scans are performed only as clinically indicated at pre-study, and for restaging as determined per investigator's discretion. For those patients who have initial progression (PD) in the first 12 weeks post-registration, a confirmation scan will be required 4 weeks later to confirm PD. See 13.6 for further details. If progression is confirmed then the date of disease progression will be the first date the patient met the criteria for progression based on standard RECIST 1.1 criteria.
- ⁶ Mandatory blood draws for research immunology studies should *not* be collected and submitted until *after* the patient is registered onto the study, but before beginning study treatment, Cycle 3, Cycle 7 and Cycle 19 or PD, withdrawal, removal, or study completion for peripheral blood mononuclear cells (PBMC) (4 times), and for serum before treatment and cycle 7 day 1 (2 times). See Section 14 and Laboratory Manual for detailed information regarding blood draws.
- ⁷ ≤ 60 days from registration. NOTE: Receipt of archival tumor tissue is not required for study registration and initiation of therapy. (Cohort 1 and 2)
- ⁸ CT-guided or ultrasound-guided tumor biopsy *after* the patient is registered onto the study, but *before* beginning study treatment. Collection of this tissue is optional for research purposes. If a patient is not willing to undergo this procedure, it does not cause the patient to be ineligible; however, collection of this tissue is **strongly encouraged** (Cohort 1; anticipate collecting samples from 20 of 30 patients)
- ⁹ Patients with $>1+$ proteinuria on dipstick urinalysis will undergo 24-hour urine collection for quantitative assessment. Patients with > 1 g/24 hours on the baseline assessment will be ineligible. See Section 8.22 for management of proteinuria.
- ¹⁰ Adverse events should be assessed at every cycle and are done prior to infusion of pembrolizumab.

- ¹¹ Patients' blood pressure diary and patient medication diary should be given to the patient on day 1 of each cycle.
- ¹² The mandatory blood sample for Cohort 2 can be drawn at any time after registration. For new patients, it must be drawn prior to the study treatment initiation. For patients who have started treatment, it must be drawn at the next treatment visit. Submit the Specimen Submission: Blood (PBMC for Cohort 2 only) Form in Rave via Add Event drop down box.
- ^R Research funded (see Section 19.0)

5.0 Grouping Factor:

- Cohort 1 vs. 2

